## **10.3** Secondary Safety/Tolerability Outcomes

In general, data for all secondary safety/tolerability outcomes are collected longitudinally across the study on complication tables at each visit and systematic collection of open-ended adverse events reported on the AE log. Secondary safety/tolerability outcomes are generally reported as a binary outcome evaluated in an aggregate fashion (e.g. through 5 years).

Treatment groups will be compared for binary safety outcomes using unadjusted chi-squared tests or Fisher's exact tests for rare events with expected cell counts < 5.. Risk differences with 95% CIs are based on Mantel-Haenszel estimates for the risk difference with Wald-type CIs. For events with expected cell counts < 5, the exact risk difference and 95% CI are obtained by exact methods based on the score statistic based on Chan and Zhang (ref Chan, Zhang 1995). Where specified, Binomial 95% CIs for proportions are based on the exact Clopper-Pearson method (ref Clopper, Pearson). These are the same methods as used for aggregate binary efficacy outcomes.

Maximum dindo score will be analyzed as an ordinal outcome with an unadjusted Mantel-Haenszel chi-squared mean score test with standardized midranks scoring (MODRIDIT option in SAS).

For any continuous or binary safety outcomes measured and analyzed as repeated measures, the same Mixed models as specified for efficacy assessments will be used. Continuous or ordinal safety outcomes assessed at a single timepoint, mean differences, 95% CIs, and *P* values are unadjusted and based on *t* tests for normally distributed continuous outcomes, and *P* values for non-normal continuous outcomes (summarized with medians) are from Wilcoxon Rank Sum tests.

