#### 4.1 Overall Study Design and Plan

The study is a multi-center randomized, surgical trial of women with symptomatic post-hysterectomy apical (cuff) prolapse desiring surgical treatment. This study will compare the three available surgical treatments performed in usual practice. The purpose of this study is to compare two commonly performed mesh apical repairs (sacral colpopexy vs. Apical Transvaginal Mesh) and vaginal native

tissue apical repairs. The primary outcome is measured over time (up to 60 months) using a survival analysis approach.

Participants are followed in ASPIRe until the last participant reaches 36 months of follow-up, so at study completion, participants will have variable follow-up between 36 and 60 months.

A study schematic is shown below:

\*All groups may receive concomitant anterior and/or posterior repairs and full-length mid-urethral slings as indicated, per the discretion of the surgeon.

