				The outcome will then be computed as the difference in score at each timepoint's corresponding attended post- operative visit and the score at baseline. If data for the assessment are missing at a timepoint's corresponding attended post-operative visit, the outcome variable will be coded as missing.
Indicator of new or worsening stress urinary incontinence (SUI)	CRF-12, CRF-13, CRF-96	Binary	surgery through 3 years	Through the timepoint of follow-up, based on the Adverse Event Log (CRF-96) or specific complications as reported on the masked post-operative CRF-12 and coordinator follow-up CRF-13 collected at 6-weeks and in 6-month intervals through 3 years, the indicator is defined as follows:
				1 = Yes, if new or worsening SUI is reported as evident (i.e. response of "AE", "SAE") on any of the complication tables as described above or "Stress urinary incontinence"" in the term reported on the AE Log

				0 = No, else if subject attended at least one post- operative visit 6 weeks or after and complication(s) of interest specified above are reported as "Not Evident" across all attended post-operative visits. Subjects with missing responses are included as long as the subject has at least one "Not Evident" response (assuming low missing response rate among attended visits).
				. = Missing, otherwise
				*Note: Prior to and upon database lock, any stress urinary incontinence events identified by the MedDRA coded preferred term "stress urinary incontinence") with start date after surgery collected ONLY on the AE log and not reported on any of the complications tables will be assessed, and if any, included in this definition at the discretion of the principal investigator.
Indicator of new or worsening urgency urinary incontinence (UUI)	CRF-12, CRF-13, CRF-96	Binary	surgery through 3 years	Through the timepoint of follow-up, based on the Adverse Event Log (CRF-96) or specific complications as reported on the masked post-operative CRF-12 and coordinator follow-up CRF-13 collected at 6-weeks and in 6-month intervals through 3 years, the indicator is defined as follows:
				1 = Yes, if new or worsening UUI is reported as evident (i.e. response of "AE", "SAE") on any of the complication tables as described above or "Urge incontinence" in the term reported in the AE log.

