## **10.2** Safety and Tolerability Variables

Variable	CRF Source	Туре	Timepoint(s)	Definition
Secondary Safety and Toler	ability Outcon	mes		
Indicator of prolapse mesh exposure in the anterior vagina	CRF-8, CRF- 10/12, AE log	Binary	Post-surgery through last visit	
 
Through the timepoint of follow-up, the indicator is defined as follows:
 
1 = Yes, if mesh exposure in vagina is reported as evident (i.e. response of "AE", "SAE") and Anterior=Yes and Description of Management of Mesh Exposure indicates the mesh was "from/for Prolapse Surgery" (case insensitive) on any of the complication tables as described above
 
0 = No, else if subject attended at least one post-operative visit 6 weeks or after and complication(s) of interest specified above are reported as "Not Evident" across all attended post-operative visits. Subjects with missing responses are included as long as the subject has at least one "Not Evident" response (assuming low missing response rate among attended visits).
 
. = Missing, otherwise
 

Indicator of prolapse mesh exposure in the posterior vagina	CRF-8, CRF- 10/12, AE log	Binary	Post-surgery through last visit	
 
Through the timepoint of follow-up, the indicator is defined as follows:
 
1 = Yes, if mesh exposure in vagina is reported as evident (i.e. response of "AE", "SAE") and Posterior=Yes and Description of Management of Mesh Exposure indicates the mesh was "from/for Prolapse Surgery" (case insensitive) on any of the complication tables as described above
 
0 = No, else if subject attended at least one post-operative visit 6 weeks or after and complication(s) of interest specified above are reported as "Not Evident" across all attended post-operative visits. Subjects with missing responses are
 

				<pre>included as long as the subject has at least one "Not Evident" response (assuming low missing response rate among attended visits).</pre> . = Missing, otherwise
exposure in the distal (lower half/introitus) vagina	CRF-8, CRF- 10/12, AE log	Binary	Post-surgery through last visit	Through the timepoint of follow-up, the indicator is defined as follows:         1 = Yes, if mesh exposure in vagina is reported as evident (i.e. response of "AE", "SAE") and distal (lower half/introitus)=Yes and Description of Management of Mesh Exposure indicates the mesh was "from/for Prolapse Surgery" (case insensitive)         on any of the complication tables as described above

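### Late safety events, above all mesh exposure and erosion, are planned as crude proportions over 36 to 60 months of follow-up and so estimate neither a 3-year nor a 5-year risk

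*SAP*

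**What the plan says.** SAP 10.2 sets the time frame of the mesh exposure and erosion indicators as "Post-surgery through last visit". Most other binary safety indicators also run to the last visit, some of them counted from 12 weeks. SAP 4.1 says that "participants will have variable follow-up between 36 and 60 months".

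Each indicator is Yes if the event was ever recorded. The rule for No differs by row in SAP 10.2:

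- **Mesh exposure and erosion:** it is enough that the "subject attended at least one post-operative visit 6 weeks or after", provided that no attended visit recorded the event.
- **Pelvic pain, granulation tissue, suture exposure and erosion, vaginal bleeding, scarring, shortening:** one attended visit at 6 months or later is needed.
- **Death:** having attended surgery is enough.

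SAP 10.3 gives the form of reporting: "Secondary safety/tolerability outcomes are generally reported as a binary outcome evaluated in an aggregate fashion (e.g. through 5 years". It then says: "Treatment groups will be compared for binary safety outcomes using unadjusted chi-squared tests". Fisher's exact test is used for rare events, with crude risk differences alongside.

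Other outcomes are handled differently. The primary outcome is right-censored at the last attended visit (SAP 9.4.2). Functional complications such as stress incontinence have the time frame "surgery through 3 years" (SAP 9.3). Protocol M.3 says that secondary outcomes will be analysed with model-based approaches to deal with data missing through unequal follow-up, and leaves the details to the SAP. Safety is Secondary Aim 2 in Protocol L.2.

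**The concern.** A proportion of women with an event has a clear meaning only if every woman was watched for the same time. Here the window depends on when she was operated on and on whether she stayed in the study. A woman seen once at 6 weeks and then lost contributes to the mesh-exposure percentage exactly as a woman examined for five years without an event.

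Mesh safety is a central output of this trial. The device left the market during the trial (Protocol H.1), the protocol's background cites calls for long-term safety data, and the mid-study safety analysis in the E-ASPIRe addendum looks for information not already seen in ASPIRe. That comparison needs a starting rate tied to a stated time.

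The No rule also assumes few missing responses among attended visits. SAP 7.3 reports more missed visits than expected, and remote visits without the POP-Q examination. It is a fair inference, though not stated, that a telephone visit could not provide the vaginal examination behind a mesh finding either. The COVID sensitivity analysis in SAP 9.4.3 covers only the primary outcome.

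**Working it through.** **1. The plan's own figure.** The documents give no planned safety rate, so the accrual, follow-up and loss inputs were checked on the sample size in Protocol M.1 and SAP 6: 121 per arm, 85% power. Inputs: hazard λ = 0.1116 per year, loss η = −ln 0.95 = 0.0513 per year, 2 years of uniform accrual, 3 more years of follow-up, margin 1.93, one-sided alpha 0.03.

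- P(event) = λ/(λ+η) × [1 − (e^(−3(λ+η)) − e^(−5(λ+η))) / (2(λ+η))] = 0.326.
- Events in two arms: 242 × 0.3264 = 79.0.
- Power (Schoenfeld): Φ(√(79.0/4) × ln 1.93 − 1.881) = Φ(1.04) = 85.1%. Required per arm: 120.6, so 121.

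The figure reproduces, so these inputs can be carried over to safety.

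**2. How long women are observed.** The first participant reaches six years in March 2022 (E-ASPIRe addendum, Visit Schedule), so she entered about March 2016. The last surgery was on June 10, 2019 (SAP 4.4.2). That is about 39 months of accrual. The addendum says that those randomized in the first 15 months continue into year 6. Under uniform accrual (an assumption), 15/39 = 38% can reach 60 months, or 0.38 × 0.95^5 = about 30% after 5% yearly loss. Mean observed time is about 3.9 years (3.6 years with the planned 24-month accrual).

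**3. What the crude proportion estimates.** Its expected value is ∫ f(t) × A(t) × e^(−ηt) dt from 0 to 5 years. Here f is the density of event times. A(t) is the share whose administrative follow-up reaches t: 1 up to year 3, then (6.25 − t)/3.25 for 39-month accrual or (5 − t)/2 for 24-month accrual.

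The true risk and the timing of events are assumptions. The protocol's background cites mesh exposure of 2.6% in one series, erosion up to 10% long term after sacral colpopexy, and reoperation for mesh exposure of about 15%. Take a true 5-year risk of 10%.

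| Assumed event timing | True 3-year risk | Crude, 39-month accrual, 5% loss | Crude, 24-month accrual, 5% loss | Crude, no loss (39 / 24 months) |
|---|---|---|---|---|
| Constant hazard | 1 − 0.9^0.6 = 6.1% | 7.9% | 7.3% | 8.8% / 8.1% |
| Half in year 1, rest even | 5 + 5 × 2/4 = 7.5% | 8.6% | 8.2% | 9.2% / 8.8% |
| 80% in year 1, rest even | 8 + 2 × 2/4 = 9.0% | 9.3% | 9.1% | 9.7% / 9.5% |

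Every crude value lies above the 3-year risk and below the 5-year risk. With 5% loss it is 79%, 86% or 93% of the 5-year risk under 39-month accrual, and 73%, 82% or 91% under 24-month accrual. The relative shortfall therefore runs from 7% to 27%. The ratios hardly change for true 5-year risks of 5% to 15%. Without loss the shortfall is 3% to 19%.

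**4. Arm comparison (39-month accrual).** True 5-year risks of 10% and 5% differ by 5.0 points. The crude difference is about 4.0 points with constant hazard and 4.3 points with half the events in year 1. If both arms truly have 10% but lose 5% and 10% of women per year, the crude figures are 7.9% and 7.1%, a spurious gap of 0.8 points.

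**5. A 36-month cut alone.** With constant hazard λ = −ln 0.9 / 5 = 0.0211, the crude proportion cut at 36 months is λ/(λ+η) × (1 − e^(−3(λ+η))) = 5.7%, against a true 3-year risk of 6.1%. Women lost early would still count as event-free.

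**The case against.** Several points on the other side stand.

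- **The label.** The SAP's time frame is the last visit. Five years appears in SAP 10.3 as an example, and elsewhere as the longest collection period. No planned display in SAP 14 calls these 5-year risks, and follow-up durations are to be tabulated. A reader might infer that the trial will publish understated 5-year risks, but the documents do not say so. A percentage labelled as crude incidence over 36 to 60 months is not misstated.
- **The direction.** A reader might call the figures biased low without qualification. They are low only against a 60-month target. Against 3 years, the horizon named in the primary aims, they are high.
- **The No rule.** It would be wrong to apply the 6-week rule to pelvic pain and the others listed with it. With no event recorded, a woman seen only at 6 weeks is missing for those. Pain scores are changes from baseline, with mixed models provided for repeated measures.
- **Arm imbalance by design.** The last entrants went only to SC or NT, so TVM follow-up is slightly longer. Only 18 women were pending in April 2019. If about six TVM places moved to the other arms, crude risks of 7.6% against 7.5% would be expected (2% per year hazard, 39-month accrual, 5% loss), which is negligible.
- **The 3-year functional outcomes.** SAP 9.5.1 generally limits secondary efficacy outcomes collected over several visits to three years. That is a choice, not a contradiction with safety.
- **Status.** SAP 7.7 makes secondary p-values and intervals descriptive. The 5% loss is the design's ceiling, and the addendum reports excellent follow-up so far.

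These points limit the size and the wording of the concern. They do not give the planned percentage a time frame, and a descriptive rate still needs one.

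**Conclusion.** The point holds for late-occurring binary safety outcomes, chiefly mesh exposure and erosion. The planned proportion is a mixture over unequal follow-up and estimates neither a 3-year nor a 5-year risk.

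Read as a 5-year risk, it is low by roughly 7% to 27% in relative terms. That range rests on an assumed 5% yearly loss, uniform accrual over 24 or 39 months, non-informative loss and three assumed event-time shapes. It is smaller with less loss and near zero for intraoperative and perioperative events. No single value within it can be drawn from the documents. With similar follow-up across arms, differences shrink toward zero but do not reverse. Loss that differs by arm would bias them.

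The plan also falls short of Protocol M.3, which names unequal follow-up as the reason for model-based secondary analyses. SAP 10.3 has no follow-up term for these indicators. The primary efficacy analysis is unaffected.

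**What to change.** Keep the planned counts and percentages, and label them as crude incidence over 36 to 60 months of follow-up.

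For mesh exposure, mesh erosion and the other late complications, add:

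- cumulative incidence by arm at 36 months, and descriptively at 60 months, censored at the last attended visit and with death as a competing event;
- arm differences with confidence intervals from those estimates;
- person-time by arm.

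Do not replace the full-follow-up totals with a 36-month cut. That would drop later mesh events from the report and, as step 5 of the working shows, would still count women lost early as event-free.

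The cost is modest extra programming. Visit schedules and adverse-event onset dates are already collected. One limitation should be stated with the results: an event found at a visit is known only to lie between that visit and the one before it.

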# **10.4** Deaths and Serious Adverse Events

A serious adverse event (SAE) is defined as any event that occurs during the 'active' phase of treatment, or the follow-up periods, and either: (1) results in death, or (2) requires inpatient hospitalization or a prolongation of existing hospitalization, or (3) is a congenital anomaly/birth defect, or (4) results in persistent or significant disability / incapacity, or (5) is life-threatening, or (6) requires intervention to prevent one of the above outcomes.

MedDRA SOC and preferred term for SAEs, treatment-related SAEs and SAEs with an outcome of death will be summarized by treatment arm.

## **10.5** Other Safety Outcomes

All AEs identified on the AE forms will be summarized by treatment arm using MedDRA-classified preferred terms and system organ class with numbers and percentages summarized by treatment arm.

# 11 ANALYSIS OF OTHER OUTCOMES

No analyses of outcomes other than efficacy and safety/tolerability outcomes are planned.

## 12 UPDATES TO ORIGINAL STATISTICAL ANALYSIS PLAN

With Version 2 of this SAP (February 20, 2023), the following clarification and addition were made to the original version.

### Clarification to Section 9.4.2 Test of Proportionality Assumption:

Due to limitation of the SAS procedure and the use of the ID statement, the likelihood ratio test was conducted comparing nested semi-parametric interval censored models analogous to the primary efficacy analysis methods (but further relaxing the piecewise constant hazard assumption to be unspecified--no parametric assumptions made on the baseline hazard only that it is proportional).

Addition to Section 9.4.3 Sensitivity Efficacy Analyses of Primary Outcome

### Post-hoc Sensitivity Analysis excluding data after the 3 year visit

A sensitivity analysis of the primary outcome through the primary endpoint excluding data after the 3 year visit on the primary analysis population will be conducted to evaluate the proportional hazards assumption during the first 3 years. Failure probability, hazard rate, and hazard ratio estimates and their corresponding confidence intervals and p-values are from an interval-censored proportional hazard model with an assumed underlying piecewise exponential hazard with three constant-hazard periods: [0, 12], (12, 24], (24, 36]. Excluding follow-up years 4 and 5 removed 14 events (2 events in NTR, 5 events in SC, and 7 events in TVM). The proportional hazards assumption is not violated in the MITT population (p=0.155).

### 14 LIST OF POTENTIAL DISPLAYS

Data displays may be added, deleted, rearranged or the structure may be modified after finalization of the SAP. Such changes require no amendment to the SAP as long as the change does not contradict the text of the SAP. Specific display shells will be generated and reviewed by the protocol team prior to the initiation of analyses.

Potential list of displays for the primary manuscript are as follows: Table and figure shells are in a separate document.

### Tables – in manuscript

Table 1 Baseline Characteristics in the Modified Intent-to-Treat Population

Table X Time until Surgical Treatment Failure for MITT, PP, & MITT Narrow (3 separate tables – perhaps put some or all in online supplement, depending on results)

Table 2 Secondary Efficacy, Safety/Tolerability and Masking Outcomes in the Modified Intentto-Treat Population

Table 3 Secondary Efficacy, Safety/Tolerability and Masking Outcomes

### Figures – in manuscript

Figure 1 Consort Diagram

Figure 2 Failure Probability for the Primary Outcome Comparing Native Tissue, Sacral Colpopexy, and Transvaginal Mesh in the Modified Intent-to-Treat Population (4-panel figure showing (a) 3-line survival plot with no confidence intervals of testing, (B-D): each of the pairwise tests with confidence intervals and showing modeling results. Panel for TM vs SC will either be of non-inferiority, or if that is accepted, with be for superiority. Pairwise plots may need to use different applicable populations than the 3-way summary plot.

Figure 3 Distribution of the Composite Surgical Failure Outcome in the Modified Intent-to-Treat Population ("ASSORT diagram")

### **Online Supplement**

eFigures 1-3. Diagram of each of the 3 surgical procedures

eFigure 4. Pelvic Organ Prolapse Quantification (POPQ) Schematic

eTable 1 Analysis Populations and Visit Completion - All Randomized Participants

eTable XX follow-up durations and COVID timing by calendar time of enrollment

eTable 1A Data Collection/Completeness of Primary Efficacy by Randomized Treatment Group

eTable 1B Primary Outcome (First Event Incorporated) Completeness by Randomized Treatment Group

eFigure Y. Failure Probability for the Primary Outcome in the Per-Protocol Population

eFigure Z. Failure Probability for the Primary Outcome in the MITT-Narrow

eFigure 9. Distribution of Surgical Failure Outcome among Participants with Intermittent Failures in the Modified Intent-to-Treat Population

eFigure 4. Assumption Check: Smoothed Hazard Rates for the Primary Outcome

eFigure 5. Assumption check: Estimated Log Cumulative Hazard by Log-Time for the Primary Outcome

eTable X. Sensitivity Analysis: Failure Probability for the Primary Outcome in primary populations with further reduction of patients enrolled after FDA order to stop mesh.

eTable X. Sensitivity Analysis: Unadjusted Failure Probability for the Primary Outcome

eTable X. Sensitivity Analysis: Failure Probability for the Primary Outcome adjusting for enrollment cohort

eTable X. Sensitivity Analysis: Hazard Ratio for the Primary Outcome with Random Site Effect

eTable 2 Concomitant procedures in the Modified Intent-to-Treat Population

eTable 3 Perioperative outcomes in the Modified Intent-to-Treat Population

eTable 4. Sexual Function and Dyspareunia Results from PISQ-IR a in the Modified Intent-to-Treat Population by Randomized Intervention

eTable 5. Adverse Events by System Organ Class and Preferred Term in Safety Population by Received Surgical Intervention

eTable 6. Serious Adverse Events by System Organ Class and Preferred Term in Safety Population by Received Surgical Intervention

# 15 ATTACHMENTS

## 15.1 Attachment 1: Scoring of the SF-12 PCS and MCS Subscales

The scoring of the SF-12 QOL assessment was found at

https://drhays.dgsom.ucla.edu/files/view/docs/programs-utilities/sf12v1\_short.sas.txt. This attachment provides a summary of the calculations for both the Physical Component Summary (PCS) and Mental Component Summary (MCS) subscales of the SF-12.

The SF-12 is comprised of 12 questions. Q1, Q8, and Q12 use five-number scales; Q4 through Q7 use yes/no scales; and Q 2 and Q3 have three-number scales; and Q9 through Q11 use sixnumber scales. For Q1 and Q8, values are assigned to each response as follows: 100=excellent, 75=very good, 50=good, 25=fair, 0=poor. For Q12, values are assigned to each response as follows: 100=none of the time, 75=a little of the time, 50=some of the time, 25=most of the time, 0=all of the time. Q2 and Q3 receive values as follows: 0=yes, limited a lot; 50=yes, limited a little; 100=no, not limited at all. For Q4-Q7, values are assigned as follows: 0=yes and 100=no. For Q9 and Q10, values are assigned to each response as follows: 100=all of the time, 80=most of the time, 60=a good bit of the time, 40=some of the time, 20=a little of the time, 0=none of the time. For Q11, values are assigned to each response as follows: 0=all of the time, 20=most of the time, 40=a good bit of the time, 60=some of the time, 80=a little of the time, 100=none of the time.

With values assigned to each question, the raw PCS and MCS scores are then calculated as a weighted sum based on the assigned value for each question. The weights are provided in Table A-1 and Table A-2. The PCS and MCS subscales are then calculated by multiplying these sums by 10 and adding a constant to each raw score (PCS=56.57706, MCS=60.75781).

Question	Assigned Value						
Number	0	20-25	40	50	60	75-80	100

 Table A-1. Sum Weights for Question Values – PCS

Version 1.0, 8/17/2022; Page 88

	1			1			
1	-8.37399	-5.56461		-3.02396		-1.31872	0
2	-7.23216			-3.45555			0
3	-6.24397			-2.73557			0
4	-4.61617						0
5	-5.51747						0
6	3.04365						0
7	2.32091						0
8	-11.25544	-8.38063		-6.50522		-3.80130	0
9	3.46638	2.90426	2.37241		1.36689	0.66514	0
10	-2.44706	-2.02168	-1.61850		-1.14387	-0.42251	0
11	4.61446	3.41593	2.34247		1.28044	0.41188	0
12	-0.33682	-0.94342		-0.18043		0.11038	0

 Table A-2. Sum Weights for Question Values – MCS

Question Number	Assigned Value									
	0	20-25	40	50	60	75-80	100			
1	-1.71175	-0.16891		0.03482		-0.06064	0			
2	3.93115			1.86840			0			
3	2.68282			1.43103			0			
4	1.44060						0			
5	1.66968						0			
6	-6.82672						0			
7	-5.69921						0			
8	1.48619	1.76691		1.49384		0.90384	0			
9	-10.19085	-7.92717	-6.31121		-4.09842	-1.94949	0			
10	-6.02409	-4.88962	-3.29805		-1.65178	-0.92057	0			
11	-16.15395	-10.77911	-8.09914		-4.59055	-1.95934	0			
12	-6.29724	-8.26066		-5.63286		-3.13896	0
